4.3 Software

The tables, listings, figures and any non-descriptive statistical analysis will be produced using SAS® Software (Version 9.3 or higher). The REPORT procedure (SAS PROC Report) will be used to produce all tables and listings; SAS/GRAFH will be used to produce all figures.

All tables, listings, and graphs will be produced to landscape orientation using Courier New 9pt font and will be incorporated into a MS Word document as a (RTF) rich text file (margins on standard A4: Margins (top, left, right, and bottom) 2.54 cm.

4.4 Study Patients

4.4.1 Disposition of Patients

The patient disposition including the date the informed consent was signed, date of last infusion of study drug and the primary reason for discontinuation of study treatment will be listed. Moreover, the number of patients who consented to the study, were exposed to study treatment and primary reason for end of treatment will be summarized.

Those patients who did not meet the eligibility criteria or were screen failures will be listed.

A listing of patients included into each of the analysis set will be presented, related summary statistics will be provided.

A clear accounting of the disposition of all patients who enter the study will be provided, from screening to study completion.

4.4.2 Protocol Deviations

A protocol deviation is any change, divergence, or departure from the study design or procedures of a study protocol. All protocol deviations will be listed by patient. All protocol deviations will be discussed during Data Review Meeting (DRM) and addressed with the “final” classification together their overall effect on a patient, as well, assignment of each patient to the analysis sets will be decided. During DRM, all protocol deviations and their possible impacts will be discussed

PAREXEL International
Statistical Analysis Plan Template for Early Phase Studies

Symphogen A/S

Sym013-01

between PAREXEL and Symphogen and will be assessed as “minor” or “major”. Major protocol deviations and protocol deviations affecting primary analyses can lead to the exclusion of a patient from the analysis sets. Reasons for excluding patients from any analysis set will be reported and described in the DRM Report that will be finalized before database hard lock and signed off by all relevant scientific experts.

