3.2.4 Summary of Clinical Findings

3.2.4.1 Protocol Sym013-01

This is the first clinical trial to study Pan-HER. As of Amendment 6, a total of 19 patients have been entered to Part 1 of this trial: 1 patient each at 1 mg/kg and 2 mg/kg weekly (Q1W), 4 patients at 4 mg/kg Q1W, 3 patients at 6 mg/kg every second week (Q2W), 7 patients at 9 mg/kg Q2W, and with Amendment 5, 3 patients at the recently initiated cohort of 9 mg/kg Q2W + mandatory intensive prophylaxis for infusion-related reactions (IRRs) and oropharyngeal mucositis. Adverse events (AEs) observed at the 4 mg/kg Q1W dose activated the stopping rule of the single-patient dose cohort titration and resulted in transition to a 3+3 trial design. Effective with Amendment 3, due to Grade 1-2 oral mucositis, rash, and diarrhea at the 4 mg/kg Q1W dose, the dosing interval in this trial was changed from Q1W to Q2W for doses of 6 mg/kg and higher. Overall, the most frequently occurring, treatment-related AEs have been IRRs, oral mucositis, rash, and diarrhea.

Regarding IRRs, despite required premedication with a glucocorticoid and an antihistamine, 2 of 4 patients at 4 mg/kg Q1W experienced Grade 1-2 events, and 2 of 3 patients at 6 mg/kg Q2W experienced Grade 2 events. Per protocol, the occurrence of 2 IRRs in the 6 mg/kg Q2W cohort resulted in prolongation of infusion from a minimum duration of 2 hours to 2.5 hours, beginning with the 9 mg/kg cohort. Two (2) of the first 4 patients at 9 mg/kg Q2W experienced Grade 1-2 IRRs, and a fifth patient experienced a Grade 3 IRR. The Grade 3 event met the protocol-specified DLT criteria and was reported as a study drug-related serious adverse event (SAE). The patient was discontinued from study and the 9 mg/kg Q2W cohort was expanded. In addition, the minimum duration of infusion for subsequent patients was once again extended, from 2.5 hours to 3 hours, and as allowed per protocol, additional premedications were recommended for all future patients, to include predosing with montelukast and oral

Confidential Page 27 of 156

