As of Amendment 5: As described, 2 events meeting the protocol DLT criteria occurred in the 9 mg/kg Q2W cohort, IRR and mucositis, and while increased prophylaxis for each was recommended, it was not fully implemented in advance of these events. For this reason, intensive prophylaxis for both toxicities was made mandatory in an effort to facilitate a more accurate evaluation of the safety and tolerability of Pan-HER at dose levels likely to be therapeutically active. Per amendment, patients entered to receive 9 mg/kg Q2W in Dose Level 5P (P=prophylaxis) and patients entered thereafter must receive intensive prophylaxis, as defined herein, on a mandatory basis to reduce the risk of IRRs and oropharyngeal

Confidential Page 28 of 156

mucositis. Further, to reduce the risk of IRRs the infusion duration of Pan-HER was further prolonged, with delivery over a fixed 4-hour period (unless further prolongation is required for an individual patient due to the occurrence of an IRR). Titrated rate increases during infusions and infusion duration reductions after C1/D1 were no longer allowed.

As of Amendment 6: With Amendment 3, Q1W dosing was halted; with Amendment 6, Q1W dosing is reintroduced under the prophylaxis and infusion duration conditions outlined in Amendment 5. All patients must receive intensive prophylaxis, as defined herein, on a mandatory basis to reduce the risk of IRRs and oropharyngeal mucositis, and must receive Pan-HER infusions over a fixed (at minimum) 4-hour (+10 min) period, unless further prolongation is required for an individual patient due to the occurrence of an IRR. Reevaluation of Q1W dosing will begin at the 6 mg/kg dose; however, lower doses may be explored if indicated based on tolerability.

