6.4 Replacement of Patients

6.4.1 Part 1, Dose-Escalation Cohorts

Patients in Part 1, who do not complete Cycle 1 as defined in **Section 9.5.2**, for reasons other than drug toxicity, will be replaced.

Data from these patients will be included in the safety analysis, but will not contribute to the determination of the MTD.

Confidential Page 53 of 156

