Additional Patients: There is the potential for additional patients to be enrolled in the dose-escalation portion of the trial to ensure a sufficient number of evaluable patients per cohort by entering an additional patient to a cohort (e.g., increase a 1 patient cohort to 2 patients, a 3 patient cohort to 4 patients, or a 6 patient cohort to 7 patients).

Note: Should this action be taken, cohort tolerability assessment and subsequent dose-escalation will occur when the minimum number of patients required to evaluate tolerability have completed Cycle 1. However, if any additional patient experiences an event that would, per protocol, result in either cohort expansion or the halting of dose-escalation, protocol rules as outlined herein will be followed.

Escalation Rules: Escalation from a current dose level to the next will only proceed following evaluation of tolerability of the current dose level. Thus, dosing of the first patient at any new dose level will commence only after all patients to be treated at the current dose level have completed Cycle 1, and the current dose level has been found to be tolerable. The dose-escalation decision points are listed below:

- If no DLTs are encountered in any of the first 3 patients completing Cycle 1 within a dose level, dose-escalation may continue to the next level
- If 1 of 3 patients within a dose level experiences a DLT, 3 more patients will be enrolled at the same dose level (to a total of 6 patients). If no DLTs are encountered in the 3 additional

Confidential Page 58 of 156

patients, dose-escalation may continue to the next level when all patients have completed and tolerated Cycle 1

- If ≥2 patients within a dose level (of up to 6 patients) experience a DLT, then that dose will be considered to have exceeded the MTD and the dose level just below this MAD will be considered to be the potential MTD
- Once the potential MTD has been declared, the MTD dose level will be completed to a total of 6 patients, if not already accomplished. In order to confirm the MTD, ≤1 of 6 patients within a dose level may have experienced a DLT
- An MTD may or may not be found within the dose levels tested. Dose-escalation may be stopped due toxicity observations other than DLTs and/or results from PK and/or target engagement analyses

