10.2 Analysis Population

Two analysis sets will be defined in accordance with the consolidated ICH E9 GCP guidelines.

The Full Analysis Set (FAS) will comprise all enrolled patients who have received at least one dose of Pan-HER. The FAS will be used for evaluation of all endpoints except evaluation of DLTs. The patients in the FAS will contribute to the analyses as allocated to treatment. For the evaluation of PK endpoints, patients, full profiles, or single measurements can be excluded from the analyses. The decision of excluding patients, full profiles, or part of profiles will be described in the clinical trial report (CTR).

The DLT Analysis Set will comprise all patients in the FAS enrolled in Part 1, except patients who did not complete Cycle 1 for reasons other than drug toxicity. The DLT Analysis Set will be used for evaluation of DLTs.

Confidential Page 95 of 156

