4.5 Analysis Sets

Two analysis sets will be defined in accordance with the consolidated ICH E9 GCP guidelines.

The Full Analysis Set (FAS) will comprise all enrolled patients who have received at least one dose of Pan-HER. The FAS will be used for evaluation of all endpoints except evaluation of DLTs. The patients in the FAS will contribute to the analyses as allocated to treatment (patients will be reported below the regimen and dosage actually received). For the evaluation of PK endpoints, patients, full profiles, or single measurements can be excluded from the analyses with justification. The decision of excluding patients, full profiles, or part of profiles will be described in the clinical trial report (CTR).

The DLT Analysis Set will comprise all patients in the FAS enrolled in Part 1, except patients who did not complete Cycle 1 for reasons other than drug toxicity. The DLT Analysis Set will be used for evaluation of DLTs and the MTD or lack thereof.

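### SAP 4.4.2 lets protocol deviations remove patients from the FAS and the DLT Analysis Set once DLTs are known, contrary to SAP 4.5 and protocol 10.2

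*SAP*

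**What the plan says.** SAP 4.4.2 has the contract organisation and the sponsor grade each protocol deviation as minor or major at a data review meeting and settle there which analysis sets each patient belongs to. It then states: "Major protocol deviations and protocol deviations affecting primary analyses can lead to the exclusion of a patient from the analysis sets". Reasons go into a signed report completed before hard lock. No deviation types are named in advance.

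SAP 4.5 defines two sets and no others. On the first: "The Full Analysis Set (FAS) will comprise all enrolled patients who have received at least one dose of Pan-HER". The second is the FAS patients of Part 1, "except patients who did not complete Cycle 1 for reasons other than drug toxicity"; protocol 10.2 uses the same definition. The only other discretion in either section concerns PK evaluation. On the use of the second set, SAP 4.5 says: "The DLT Analysis Set will be used for evaluation of DLTs and the MTD or lack thereof".

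Protocol 6.4.1 covers patients replaced because they did not complete Cycle 1 for non-toxicity reasons: "Data from these patients will be included in the safety analysis, but will not contribute to the determination of the MTD".

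SAP 4.11.1 and protocol 10.3.1 both promise a listing of every DLT event, and SAP 4.2 promises listings covering all consented patients. In SAP section 6, however, Table 14.2.4.8 and Listing 16.2.7.1 are both restricted to the DLT set.

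**The concern.** The exclusion sentence adds a ground for removal that the set definitions do not contain. Because the DLT set is drawn from the FAS, removal from the FAS also removes a patient from the DLT set.

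The timing makes this matter. The trial is open-label and protocol 9.5.3 requires presumed DLTs to be reported within 24 hours, so those deciding membership know who had a DLT. The sentence also singles out deviations that bear on the primary analysis. With cohorts of three to seven patients, one exclusion can change the reported DLT rate and possibly the MTD statement. The direction cannot be predicted: removing a patient with a DLT lowers the rate, and removing one without raises it. Exclusions from the FAS would also alter every FAS-based safety and efficacy table.

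The listing population compounds the problem. A patient outside the DLT set who had a DLT would be missing from both the DLT table and the DLT listing, despite the promise to list every event.

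**Working it through.** The SAP gives no sample size, power or error rate for this point, so there is no planned figure to reproduce. The check compares the membership rules and then works out what one exclusion does to a reported cohort.

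**Membership rules side by side**

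| Source | FAS | DLT Analysis Set |
|---|---|---|
| Protocol 10.2 | Enrolled, at least one dose | Part 1 FAS, minus non-toxicity non-completers of Cycle 1 |
| SAP 4.5 | Same | Same |
| SAP 4.4.2 | Also loses patients for major deviations or deviations touching primary analyses | Same addition |

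SAP 4.14, which lists changes from the protocol's planned analysis, does not mention the added ground. Since SAP 4.5 repeats the protocol definitions, the conflict lies within the SAP itself.

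**Inputs for the example** (protocol 3.2.4.1)

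- Patients entered: "7 patients at 9 mg/kg Q2W".
- DLTs: "2 events meeting the protocol DLT criteria occurred in the 9 mg/kg Q2W cohort, IRR and mucositis". These were two different patients: the one with the IRR was discontinued, and the one with mucositis was retreated at a reduced dose.
- Assumption: all 7 are in the DLT set. The documents do not confirm this, so 6 is shown as well.

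**MTD thresholds**

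- Protocol 10.3.1: at most 1 of 6 patients with a DLT. Protocol 7.1.3.2 adds that "the MTD dose level will be completed to a total of 6 patients".
- SAP 3.1: fewer than 33% of patients with a DLT.

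**Calculation**: rate = patients with a DLT / patients in the DLT set, removing one patient at a time.

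| Case | Rate | Change (points) | At most 1 DLT | Below 33% | At least 6 patients |
|---|---|---|---|---|---|
| 7 in set, none removed | 2/7 = 28.6% | – | no | yes | yes |
| Remove one with a DLT | 1/6 = 16.7% | 28.6 to 16.7 = −11.9 | **yes** | yes | yes |
| Remove one without a DLT | 2/6 = 33.3% | 28.6 to 33.3 = +4.8 | no | **no** | yes |
| 6 in set, none removed | 2/6 = 33.3% | – | no | no | yes |
| Remove one with a DLT | 1/5 = 20.0% | 33.3 to 20.0 = −13.3 | **yes** | **yes** | no |
| Remove one without a DLT | 2/5 = 40.0% | 33.3 to 40.0 = +6.7 | no | no | no |

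Changes are computed from unrounded rates. Bold marks a change of class from the unreduced cohort. Starting from 7, the downward shift changes class only under the 1-of-6 rule and the upward shift only under the 33% rule. Starting from 6, the 1/5 result changes class under 33% and brings the count down to one DLT, but it leaves fewer than the six patients needed to confirm an MTD. On a pure count of DLTs, removing a patient without a DLT cannot turn a tolerated dose into an exceeded one.

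**The case against.** The best defence is that SAP 4.4.2 only describes how SAP 4.5 is applied. Protocol 9.5.2 and SAP 3.2.4.1 require 4 infusions (Q1W) or 2 infusions (Q2W) at the assigned dose to complete DLT observation. A missed infusion unrelated to toxicity is then both a deviation affecting the primary analysis and a ground for removal under SAP 4.5. This works for some DLT-set exclusions. It cannot explain removing a dosed patient from the FAS, and the sentence is not limited to such cases.

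Protocol 10.6 allows the SAP to describe departures from the plan, so the silence of SAP 4.14 carries limited weight. That does not resolve the conflict between SAP 4.4.2 and SAP 4.5.

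On the listing, SAP 4.2 says DLT evaluation uses the DLT set. That sentence stands among the rules for tables and descriptive statistics, so it supports the population of Table 14.2.4.8 but does not override the promise to list every DLT event. If the exclusion sentence is removed, the gap narrows to a patient who has a DLT and then fails to complete Cycle 1 for another reason. The event itself would still be in the all-consented AE listing (16.2.7.2.1).

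Several limits stand in full. No exclusion is documented, and neither DLT patient is shown to have had a major deviation. The meeting report, the analysis-set listing (16.2.3.1) and the deviation listing (16.2.2.1) would reveal any removal. The analyses are descriptive, and the class changes depend on which MTD threshold is applied.

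**Conclusion.** The concern holds: SAP 4.4.2 is wrong as written, because it permits removals that SAP 4.5 and protocol 10.2 do not, at a point where the primary outcome is known. In the 9 mg/kg Q2W example one exclusion moves the DLT rate by −11.9 or +4.8 points if all 7 patients are in the DLT set, and by −13.3 or +6.7 points if 6 are.

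The exposure is confined to the reported DLT rate, the MTD statement and, for FAS exclusions, the FAS tables. Escalation followed protocol 7.1.3.2 and is unaffected, and Part 2 did not take place. The cohort shows the size of the effect and need not decide the final MTD statement, since higher Q2W levels with prophylaxis were opened. The DLT table and listing are nevertheless both marked for the abbreviated study report, so the result will be published. This should be fixed. Confidence in the textual conflict is high; the consequence is possible, not demonstrated.

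**What to change.** Change the SAP only.

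1. In 4.4.2, replace the exclusion sentence with wording such as: *Protocol deviations do not change membership of the FAS or the DLT Analysis Set, which follows section 4.5 only. Any deviation-based exclusion is shown only as a flagged sensitivity analysis. The PK exclusions in 4.5 and 4.10.4.1 are unchanged.*
2. In section 6, base Listing 16.2.7.1 on the FAS and add a flag for DLT-set membership. Table 14.2.4.8 can stay on the DLT set, so the SAP 4.2 sentence on DLT evaluation still holds for it.

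The cost is one sentence and one listing population, with no new data and no protocol amendment. The trade-off is that patients with major deviations remain in the primary DLT analysis, and their influence is seen only in the sensitivity analysis.

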4.5 Analysis Sets

Two analysis sets will be defined in accordance with the consolidated ICH E9 GCP guidelines.

The Full Analysis Set (FAS) will comprise all enrolled patients who have received at least one dose of Pan-HER. The FAS will be used for evaluation of all endpoints except evaluation of DLTs. The patients in the FAS will contribute to the analyses as allocated to treatment (patients will be reported below the regimen and dosage actually received). For the evaluation of PK endpoints, patients, full profiles, or single measurements can be excluded from the analyses with justification. The decision of excluding patients, full profiles, or part of profiles will be described in the clinical trial report (CTR).

The DLT Analysis Set will comprise all patients in the FAS enrolled in Part 1, except patients who did not complete Cycle 1 for reasons other than drug toxicity. The DLT Analysis Set will be used for evaluation of DLTs and the MTD or lack thereof.

4.6 Demographics and Baseline Characteristics, Disease History and Prior Cancer Therapies

The following demographic and baseline variables will be recorded:

- Date of informed consent
- Date of Birth
- Gender, Race and Ethnicity
- Height
- Weight at screening and baseline

PAREXEL International
Statistical Analysis Plan Template for Early Phase Studies

Symphogen A/S

Sym013-01

- Stage at initial diagnosis and current stage
- Screening and baseline ECOG PS (categories)
- Disease history and diagnosis (Site of primary tumor, Date of initial diagnosis, Sites of metastases, Date of most recent progression)
- Prior cancer therapies including prior surgical treatment [yes/no], prior radiation therapy [yes/no] and prior systemic therapies, Prior anti-EGFR treatments [yes/no] and Responder to prior anti-EGFR treatments [Positive/Negative], Prior HER2 therapies [yes/no] and Responder to prior HER2 therapies [Positive/Negative]

Age at consent in years will be derived as (Year of informed consent signed – Year of date of birth) + 0 if the month and day of informed consent signed >= the month and day of date of birth, else + 1. The following age classes will be as well derived: < 65 years; 65 - <75 years; 75 - <85 years; 85 years or older.

BMI at baseline will be calculated as Weight [kg] / (Height [m])²

Time since initial diagnosis will be derived as (Year of informed consent signed – Year of initial diagnosis) + 0 if the month and day of informed consent signed >= the month and day of initial diagnosis, else + 1.

Number of sites with metastases will be derived by counting all sites with metastases.

Prior systemic therapies for cancer will be counted by regimen and summarized as 0, 1, 2, 3, 4+ for each patient.

Regimens containing anti-EGFR or HER2 drugs will be identified.

Demographic and baseline characteristics, Disease History and Prior Cancer Therapies will be listed.

Listing of Systemic Therapies will be reviewed by Symphogen and PAREXEL and regimens with anti-EGFR or HER 2 treatments will be flagged, data should then match with answers collected in CRF for prior anti-EGFR treatments [yes/no] and Prior HER2 therapies [yes/no]; cases of

PAREXEL International
Statistical Analysis Plan Template for Early Phase Studies

Sympogen A/S

Sym013-01

mismatch will be queried; any unsolved case of mismatch will be reviewed by on a patient by patient basis.

Descriptive continuous statistics will be presented for:

- Demographic and baseline characteristics (including age, height, weight and BMI)
- Disease History information (including Time since initial diagnosis [years]).

The frequency and percentage of patients will be tabulated for:

- Demographic and baseline characteristics categorical variables (including gender, race, and ethnicity);
- Disease History information (including ECOG PS, Site of primary tumor, number and sites of metastases, EGFR and HER2 results [positive/negative])
- Prior Cancer Therapies for current malignancy (including prior surgical treatment [yes/no], prior radiation therapy [yes/no], number of prior systemic therapies [0, 1, 2, 3, More than 3], Prior anti-EGFR treatments [yes/no] and Responder to prior anti-EGFR treatments [yes/no], Prior HER2 therapies [yes/no] and Responder to prior HER2 therapies [yes/no]).

The stage at initial diagnosis and current stage will only be listed.

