8.1.2 Demographics

To include date of birth (or year of birth/age in regions where applicable), sex, race and ethnicity.

Screening

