4.2 General Presentation Considerations

Baseline

‘Baseline’ is defined as the last available pre-treatment assessment, considering both scheduled and unscheduled assessments.

Safety assessments at Cycle 1 Day 1 with no time of assessment (i.e. Vital Signs and Body Measurements, ECOG PS, Physical Examination) are assumed to be taken pre-treatment.

End of Treatment (EOT)

‘End of Treatment’ is defined as the first assessment on or after the last dose of study treatment, considering both scheduled and unscheduled assessments.

Unscheduled assessments

Unscheduled assessments will be presented in listings in chronological order.

Post Baseline unscheduled assessments (for Clinical Laboratory, ECG QTc, etc.) will be used for determination of worst result (i.e. Maximum and Minimum post Baseline result) as well as the maximal laboratory CTCAE grade if applicable; also, all post baseline tumor evaluation assessments will be used to derive BOR.

Except considered as Baseline, EOT or worst result, unscheduled assessments will not be included in summaries.

PAREXEL International
Statistical Analysis Plan Template for Early Phase Studies

Symphogen A/S
Sym013-01

Treatment Day

‘Treatment Day’ will be calculated relative to the date of C1/D1 as follow:

- assessments taken before the first infusion of IMP

Treatment Day = Assessment Date - First IMP infusion Date

- assessments after the first infusion of IMP

Treatment Day = Assessment Date - First IMP infusion Date + 1.

Missing Data

In case of partially missing date of birth or date of diagnosis, the following rule will be applied: if year and months are known but day is missing, then the day will be imputed as 15th; in case of only year known, the day and month will be imputed as 15th June.

Specific rules for handling for missing efficacy assessments are detailed in section 4.10.1.3.

Methods for handling missing concomitant medication and adverse events dates are detailed in sections 4.8 and 3.2.4.2 respectively.

Imputations will be used to derive parameters, in listings original data will be presented as collected.

Data Listing

All original and derived parameters for all consented patients will be listed.

All listings will include scheduled and unscheduled measurements.

Unless specified otherwise, data in listings will be presented by dose regimen (Q1W or Q2W), dose group, patient, and visit (ordered by date and time within patient).

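### SAP 4.6 adds 1 where completed years need minus 1, so age at consent is 2 years too high for every patient whose birthday falls after the consent date in that year

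*SAP*

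**What the plan says.** SAP 4.6 starts from the difference in calendar years between consent and birth and adds 0 "if the month and day of informed consent signed >= the month and day of date of birth, else + 1". From the result it forms age classes with cut points at 65, 75 and 85 years.

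Time since initial diagnosis follows the same pattern from the diagnosis year, adding 0 "if the month and day of informed consent signed >= the month and day of initial diagnosis, else + 1".

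The same section lists age and time since diagnosis (in years) for continuous descriptive statistics. SAP 4.2 adds that "All original and derived parameters for all consented patients will be listed".

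For incomplete birth or diagnosis dates, SAP 4.2 imputes a missing day as the 15th, and "in case of only year known, the day and month will be imputed as 15th June". Year-only birth data are possible, because Protocol 8.1.2 describes demographics as follows: "To include date of birth (or year of birth/age in regions where applicable), sex, race and ethnicity".

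**The concern.** The else branch applies when the consent month and day come before the birth month and day, so the patient has not yet had that year's birthday. Completed age is then one less than the calendar-year difference, but the SAP makes it one more. The sign is wrong in the same way for time since diagnosis. It appears twice in the same words, so it is not a text-extraction fault.

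If the rule is coded as written, the following outputs are wrong:

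- **Age:** the summary in Table 14.1.3 and the values in Listing 16.2.4.1. Both carry the asterisk that SAP 4.14 requires for the abbreviated CSR.
- **Age classes:** any tabulation of them.
- **Time since diagnosis:** wherever it is listed. Listing 16.2.4.4.1 is the likely place and also carries the asterisk.

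Dose groups are small. Protocol 3.2.4.1 gives 1, 1, 4, 3, 7 and 3 patients at Amendment 6, so a dose-group age summary can move by up to 2 years.

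**Working it through.** The documents give no worked age value, so there is no figure of the plan's own to reproduce. The inputs are the two formulas in SAP 4.6, the imputation rule in SAP 4.2 and the patient count in Protocol 3.2.4.1.

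**Size of the error, complete dates.** Let D be consent year minus birth year.

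- Birthday on or before the consent date: SAP gives D, completed age is D, error 0.
- Birthday after the consent date: SAP gives D + 1, completed age is D - 1, error (D + 1) - (D - 1) = 2.

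The literal rule was compared with a count of birthdays actually reached, over 767,700 pairs of dates. These used seven birth years between 1930 and 1999 with every calendar day, and consent every third day over 900 days from 1 October 2016. The error was +2 in all 378,796 pairs with a later birthday and 0 in all 388,904 others. With - 1 in place of + 1 it was 0 in all 767,700.

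**Examples.**

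- Born 20 October 1953, consent 15 March 2017. SAP: 2017 - 1953 + 1 = 65. Completed age: 63. The patient moves from the under-65 class to the next one.
- Diagnosed 20 October 2016, consent 15 March 2017. SAP: 2017 - 2016 + 1 = 2. Completed years: 0.

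The age class changes only for affected patients with completed age 63-64, 73-74 or 83-84.

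**Share affected.** This assumes birthdays evenly spread over 365 days. Share = (365 - day of year of consent)/365, and mean bias = 2 × share.

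| Consent date | Share affected | Mean bias (years) |
|---|---|---|
| 15 January (day 15) | 350/365 = 96% | 1.9 |
| 1 May (day 121) | 244/365 = 67% | 1.3 |
| 15 June (day 166) | 199/365 = 55% | 1.1 |
| 15 December (day 349) | 16/365 = 4% | 0.1 |

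With consent dates evenly spread as well, the share is 364/730 = 49.9% and the mean bias 1.0 year. Protocol 3.2.4.1 reports: "As of Amendment 6, a total of 19 patients have been entered to Part 1 of this trial". For that number, 19 × 0.499 = 9.5 patients are affected, with a binomial 95% range of 5 to 14.

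**Year-only birth dates.** With 15 June imputed and consent before that day, SAP gives D + 1. The error against true completed age is +2 if the real birthday is after consent and +1 otherwise: 96% and 4% for consent on 15 January, 67% and 33% for 1 May, 55% and 45% for 14 June. From 15 June onwards the error is 0 or +1, and it comes from the imputation rather than the sign.

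**Why time since diagnosis needs a floor.** A diagnosis known only as 2017 is imputed to 15 June 2017. With consent on 15 March 2017, SAP gives 0 + 1 = 1, and changing the sign alone gives 0 - 1 = -1.

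**A separate slip of the same kind.** SAP 4.10.4.1 back-transforms the geometric-mean error bars with Exp but defines mean_Ln and sd_Ln on the base-10 scale. Take an assumed geometric mean of 10 µg/mL and geometric CV of 40%. The natural-log SD is √ln(1.16) = 0.385, and the bars are exp(2.303 ± 0.385) = 6.8 to 14.7. As worded, the base-10 mean is 1 and the SD is 0.385/2.303 = 0.167, so the bars are exp(1 ± 0.167) = 2.3 to 3.2, which do not contain the plotted mean.

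**The case against.** The sign itself is hard to defend, so the case on the other side is about reach and weight.

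- **Description only.** SAP 4.10.1 plans no hypothesis tests, 4.10.1.2 no covariate adjustment, and the only subgroup in 4.10.1.6 is tumor type. SAP 4.6 does not name the age classes among the tabulated variables. This stands and limits the consequence.
- **Time since diagnosis may hardly be reported.** Table 14.1.4, whose title fits disease history best, has no asterisk, so its summary is probably not produced for the abbreviated CSR. This stands; the flagged listing remains the likely outlet.
- **Exactly 2 years presumes completed years.** That is the usual meaning of age. For disease duration the SAP says only years; against elapsed time the excess lies between 1 and 2. The formula fits neither convention.
- **The shares rest on assumptions.** The single-date shares apply only if all patients consent on that day, and 19 is an interim count. The even-spread figure of about half is the one to use.
- **Year-only dates and the floor are remote.** No document shows a year-only birth date, and where age itself is collected no derivation is needed. A patient diagnosed in the year of consent who has already had all beneficial therapy would be unusual. The floor is a precaution.
- **Checking may catch it.** SAP 4.1 promises an independent check, and dates are listed as collected. But a checker who programs from the SAP formula would reproduce the wrong value.
- **The error-bar wording is a different matter.** Agreed: Exp and the variable names show that natural log is meant, and bars that miss the mean would be noticed.

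**Conclusion.** The rule is wrong as written. With a complete birth date, age at consent is exactly 2 years above completed age for every patient whose birthday falls after the consent date in that calendar year, and correct for all others. The same holds for time since diagnosis measured in completed years.

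Under evenly spread birthdays and consent dates, about half of the patients are affected and mean age is about 1.0 year too high. The final number of patients is not in the documents, because the trial stopped during Part 1; for the 19 entered by Amendment 6, 9 or 10 would be affected.

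Whether any output is wrong depends on literal coding, which the documents do not show. The effect is limited to baseline description and leaves the DLT, response and TTP results untouched. It should still be fixed, because the specification is certainly wrong and the age outputs are flagged for the abbreviated CSR.

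**What to change.** In SAP 4.6:

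1. Replace else + 1 with else - 1 in both the age and the time-since-diagnosis formulas.
2. Add a minimum of 0 to time since diagnosis, for imputed diagnosis dates that fall after consent.
3. Note that for a year-only birth date the corrected age can still be off by 1 year in either direction, because of the 15 June imputation.

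Separately, in SAP 4.10.4.1, replace log base 10 with natural log in both definitions, to match Exp and the variable names. As worded, only the error bars in Figures 14.2.15 and 14.2.17 would be affected.

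The cost is two sign changes, one clause, one note and two wording corrections, plus the matching code. Data collection and all other analyses stay as they are.
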